#### **INTRODUCTION**

Anatomically Uterine niche is an iatrogenic pouch-like defect at the site of previous caesarean scar due to defective tissue healing. Radiologically niche should be defined as an indentation at the site of the CS scar with a depth of at least 2 mm. A niche can be subclassified in: (1) simple niche; (2) simple niche with one branch; (3) complex niche (with more than one branch).

Uterine niche occurs in up to 70% women with previous cesarean of whom 30% are symptomatic. Reported prevalence varies: 24–70% with transvaginal sonography (TVS) and 56–84% with gel/saline instillation sonohysterography (SHG). This may be an underestimation because many women are asymptomatic and also because clinicians may not recognize niche as a cause of symptoms due to unawareness. Prevalence of 45.6% was reported in a prospective observational study (n = 371) where sonohysterography was done six months post-cesarean. Prevalence increases with increasing number of previous cesareans.  $^{(1-5)}$ 

## **Potential Risk Factors**

Niche forms due to poor healing of cesarean scar. Risk factors are: (5-8)

## 1. Factors Affecting Lower Uterine Segment:

Cervical dilatation of > 5 cm, > 5 h duration of labour and advanced fetal station predispose to large niche due to thinner or less vascularized myometrium resulting in inadequate healing.

#### 2. Level of Uterine Incision

Lower uterine incision towards the cervix results in poor healing, as mucus secreted by cervical glands interferes with myometrial approximation. Mucus accumulation gradually increases the niche size also.

Cesarean section done in advanced labour after cervical effacement and also creation of uterovesical fold of peritoneum influence the level of uterine incision.

## 3. Uterine Closure Techniques

Single-layer, decidua sparing closure technique predisposes to incomplete closure, compared to single full-thickness closure. A strong myometrial scar with proper anatomical approximation without tissue strangulation minimizes risk of niches. 

If muscular edges are thick, they are best approximated by including deeper part in the first layer and the remaining superficial cut edges in the second layer.

Non-perpendicular sutures leading to an irregular myometrial closure, locking sutures or very tight second layer leading to ischemic necrosis result in poorly healed scar predisposing to niche formation.

Thus, double-layer uterine closure using non-locking sutures is the optimal closure technique that results in thicker residual myometrium and hence potentially lower risk of niches.

Suboptimal surgical techniques: Inadequate haemostasis, tissue ischemia, devascularization and excessive tissue manipulation contribute to poor scar healing and adhesions, consequently forming niche.

## 4. Adhesions

Adhesion formation with abdominal wall pulls the uterine scar towards abdominal wall, exerting counteracting force opposite to the direction of retracting uterine scar tissue and causing impaired wound healing. This mechanism is encountered in non closure of peritoneum and creation of bladder flap that is not sutured. 

#### 5. Retroflexed Uterus

Effect of gravity on uterine corpus also increases counteracting forces. Large niches are mostly found with retroflexed uterus. 

#### 6. Patient Factors

Genetic predisposition contributes to impaired healing, inflammation, or adhesion formation, post-operative infection. 

Gestational diabetes (odds ratio, 1.73), previous caesarean (OR, 3.14) and advanced body mass index (OR, 1.06) are independent risk factors. Risk increases by 6% for every additional unit increase in body mass index. 

## **Diagnosis:**

Niche can be visualized in non-pregnant state using TVS, SHG, 3-D ultrasound, magnetic resonance imaging or hysteroscopy. An anechoic space at least 2 mm deep in the myometrium at caesarean scar site clinches the diagnosis. Niche Size and Residual Myometrium thickness are measured.

Residual myometrial thickness (RMT) is the vertical distance between uterine serosa and apex of defect. Large niches are defined when RMT is < 50%of adjacent myometrium or  $\le 2.2$  mm on TVS. Absent residual myometrium is termed a total defect. 

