## **Outcome measures:**

- 1. Incidence of occurrence of cesarean scar (cs) niche in each group.
- 2. Correlation between the depth of niche and the residual myometrium in each group.
- 3. Comparison between the thicknesses of residual myometrium to adjacent normal myometrium in each group.
- 4. Complains of niche if present.

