## IV-Comparison between two groups as regard incidence of niche

Niche is defined as an anechoic space at least 2 mm depth at the presumed site of the caesarean section scar.

The incidence of niche was higher in group I, yet it did not reach statistical significance. (P=0.087). (Table 4, Fig. 17)

Table (4): Comparison between the two studied groups regarding incidence of niche

Incidence of niche	Group I		Group II		
	No %		No	%	
Absent	89	71.2	99	79.2	
Present	35	28.0	26	20.8	
X 	1.94				
P value	0.087				

Group I. cesarean section with bladder dissection Group II: cesarean section without bladder dissection  $X^2$  = Chi square-test p was significant if  $\leq 0.05$ 

[figure not shown]

Figure (17): Comparison between the two studied groups regarding incidence of niche

[figure not shown]

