#### V- Comparison between the two groups regarding niche characteristics

[figure not shown]
Length in group I ranged from 0.3-1.1 with mean value  $0.707\pm0.23$  and in group II ranged from 0.32-1.4 with mean value  $0.570\pm0.21$ . Width in group I ranged from 0.35-1.3 with mean value  $0.737\pm0.26$  and in group II ranged from 0.4-1.12 with mean value  $0.640\pm0.19$ . There was statistical significant increase in group I than group II regarding length and width (P=0.010, 0.046). There were no statistical significant differences between the two studied groups regarding depth, AMT and RMT (P= 0.421, 0.441, 0.378). (Table 5, Fig. 18)

Table (5): Comparison between the two studied groups regarding niche characteristics.

Niche characteristics	Group I	Group II	T test P value
Length (cm)			
Range	0.3-1.1	0.32-1.4	0.010+
Mean	0.707	0.570	0.010*
SD	0.23	0.21	
Width (cm)			
Range	0.35-1.3	0.4-1.12	0.046*
Mean	0.737	0.640	0.040*
SD	0.26	0.19	
Depth (cm)			
Range	0.21-0.80	0.20-0.49	0.421
Mean	0.331	0.317	0.421
SD	0.15	0.09	
AMT			
Range	0.85-1.6	0.92-1.39	0.441
Mean	1.109	1.115	0.441
SD	0.16	0.14	
RMT			
Range	0.24-1.4	0.34-0.92	0.378
Mean	0.716	0.701	0.376
SD	0.21	0.15	

Group I. cesarean section with bladder dissection Group II: cesarean section without bladder dissection t-test = student t-test p was significant if  $\leq 0.05$  \* = Significant at level 0.05

[figure not shown]

Figure (18): Comparison between the two studied groups regarding niche characteristics.

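### Residual myometrium is never set against adjacent myometrium woman by woman: no RMT/AMT ratio and no count of large niches is reported, although the printed ranges imply at least one large niche per arm

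*Protocol*

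**What the plan says.** The protocol's Diagnosis section gives two alternative criteria for a large niche: "Large niches are defined when RMT is < 50%of adjacent myometrium or" an RMT of at most 2.2 mm on transvaginal scan. It calls absent residual myometrium a total defect. Under Outcome measures, the third item reads: "Comparison between the thicknesses of residual myometrium to adjacent normal myometrium in each group".

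The SAP document, which already contains results, handles the scar in two tables.

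- **Table 4** (section IV) is a yes/no count: "Niche is defined as an anechoic space at least 2 mm depth at the presumed site of the caesarean section scar". It shows 35 women with a niche in group I and 26 in group II.
- **Table 5** (section V) gives range, mean and SD for length, width, depth, AMT and RMT, each compared between arms on its own row. The text concludes: "There were no statistical significant differences between the two studied groups regarding depth, AMT and RMT (P= 0.421, 0.441, 0.378".

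No SAP table gives an RMT/AMT ratio, a count of large niches or a count of total defects.

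**The concern.** Outcome 3 concerns a relation between two measurements in the same woman. Two separate comparisons of means, one for AMT and one for RMT, do not address it. They show whether the average residual thickness differs between arms. They do not show how much of the adjacent thickness remains in each woman, or how many women fall below the protocol's own cut-off.

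Table 4 cannot fill the gap, because it counts every niche of 2 mm or more alike. Table 5 appears to cover only women with a niche, a subgroup formed after randomisation, so its means are not a comparison of the randomised arms. A reader who wants to know whether either technique leaves more large niches per woman randomised finds no answer, although the measurements needed have been taken.

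**Working it through.** The documents print no large-niche count, so there is no figure to reproduce. The check asks what Table 5 already implies.

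**Inputs (Table 5; numbers with a niche from Table 4)**

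| | Group I | Group II |
|---|---|---|
| Women with a niche | 35 | 26 |
| RMT range | 0.24–1.4 | 0.34–0.92 |
| RMT mean (SD) | 0.716 (0.21) | 0.701 (0.15) |
| AMT range | 0.85–1.6 | 0.92–1.39 |
| AMT mean (SD) | 1.109 (0.16) | 1.115 (0.14) |

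**Step 1. Which women are in Table 5?** It prints no denominators. Equal-variance t-tests from the means and SDs with n = 35 and 26 give one-sided P = 0.379 for RMT (printed 0.378) and 0.440 for AMT (printed 0.441). With 125 per arm they give 0.258 and 0.376. The depth ranges also start at 0.21 and 0.20 cm, just at the 2 mm niche threshold. Both facts point to women with a niche only. The printed depth P value (0.421) is not reproduced with either set of denominators, so this remains an inference. The match is to one-sided tests (two-sided 0.76 and 0.88), and the SAP states no sidedness. That is a separate matter and does not change the non-significance.

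**Step 2. Unit and meaning of AMT.** AMT is not expanded, and the AMT and RMT rows carry no unit. Depth plus RMT should be near the adjacent wall thickness if all are in cm: 0.331 + 0.716 = 1.047 against AMT 1.109 in group I, and 0.317 + 0.701 = 1.018 against 1.115 in group II. This is consistent with AMT being adjacent myometrial thickness in cm.

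**Step 3. Lower bound on large niches.** The woman with the smallest RMT in an arm has an AMT no smaller than that arm's minimum, so her ratio is at most min(RMT)/min(AMT).

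- Group I: 0.24/0.85 = 0.282 (with rounding, at most 0.245/0.845 = 0.290).
- Group II: 0.34/0.92 = 0.370 (with rounding, at most 0.345/0.915 = 0.377).

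Both are below 0.50 however the values are paired. Each arm therefore has at least one large niche by the 50% criterion.

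**Step 4. The other grades.** The smallest RMT is 2.4 mm in group I and 3.4 mm in group II. Both exceed 2.2 mm and zero, so nobody in these rows meets the absolute criterion or has a total defect.

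**Step 5. Upper bound.** Let D = RMT − 0.5 × AMT; by the 50% criterion a niche is large when D < 0. One-sided Chebyshev gives P(D < 0) ≤ s²/(s² + m²), with m and s the mean and SD of D. The correlation is not given; the worst case, −1, gives s = SD(RMT) + 0.5 × SD(AMT).

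- Group I: m = 0.716 − 0.5545 = 0.1615; s = 0.21 + 0.08 = 0.29. The bound is 0.0841/(0.0841 + 0.0261) = 0.763, and 0.763 × 35 = 26.7, so at most 26.
- Group II: m = 0.701 − 0.5575 = 0.1435; s = 0.15 + 0.07 = 0.22. The bound is 0.0484/(0.0484 + 0.0206) = 0.70, and 0.70 × 26 = 18.2, so at most 18.

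**Step 6. What the means show.** The ratios of means are 0.716/1.109 = 0.646 and 0.701/1.115 = 0.629. Both are well above 0.50, so the means give no sign of the women found in Step 3.

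**Step 7. Plausible size (illustration only).** Assume RMT and AMT are bivariate normal with correlation 0 to 0.9. The expected count then falls from about 8.3 to 4.5 of 35 in group I and from about 5.0 to 1.6 of 26 in group II.

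**The case against.** The strongest reply is that no pre-specified analysis is broken. The large-niche definition is cited background. It does not appear in the aim, the methods or the outcome list. The aim is the incidence of scar defect, and Table 4 reports that with the protocol's own 2 mm definition. This stands: the count of large niches would be a post hoc addition. What remains is outcome 3, which is listed, and which separate rows for AMT and RMT do not answer.

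The documents do not support several stronger readings that a reader might infer.

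- *Group I has the more severe scars.* It has the lower minimum RMT (0.24 v 0.34) and the greater maximum depth (0.80 v 0.49 cm). It also has the higher maximum RMT (1.4 v 0.92), more niches and a larger RMT SD. Wider extremes in both directions are then expected, and single values do not show a difference between arms.
- *Every niche could be large.* Mean RMT would then lie below 0.5 × 1.109 = 0.555 in group I and 0.5 × 1.115 = 0.558 in group II; the printed means are 0.716 and 0.701.
- *The two criteria conflict, because one is met and the other is not.* They are alternatives, so this is allowed.
- *The Diagnosis section names large niches as a particular harm.* It gives imaging terms and cut-offs, and ties them to no symptom or prognosis.
- *Severe cases were concealed.* The printed ranges are what reveal them; they are uncounted.

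**Conclusion.** The point holds as a gap in reporting against outcome 3 and as an inexpensive improvement. It does not show a broken endpoint or a difference between arms. On the printed figures, large niches by the 50% criterion number between 1 and about 26 of 35 in group I, and between 1 and about 18 of 26 in group II. No woman meets the 2.2 mm criterion and none has a total defect.

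These bounds rest on AMT being adjacent myometrial thickness and on both rows sharing unit (cm), women and visit. The numbers with a niche come from Table 4. The protocol plans scans at 3 and 6 months, and Table 5 does not say which it reports.

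**What to change.** 1. Reconcile group I in Table 4 first: 89 + 35 = 124, and the printed 71.2% and 28.0% add to 99.2%. Otherwise the unclassified woman is silently counted as having no large niche.
2. Derive RMT/AMT for each woman with a niche, at a named visit, and report the ratio by arm. This answers outcome 3. Expand AMT and state the unit.
3. Beside Table 4, report per arm, over randomised women, the number with RMT/AMT below 0.50, with RMT at most 2.2 mm, with either, and with a total defect. Give a risk difference and 95% CI for large niches, and state how unclassified women are handled.
4. Label this count as a descriptive, post hoc use of the protocol's own cut-off.
5. Word the Table 5 result as *no statistically significant difference in mean RMT among women with a niche*, and do not word it as equality.

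The cost is one derived variable and a few table rows, with no new measurement. The drawback is imprecision. If, for illustration, the counts were 8/125 and 4/125, the risk difference would be 3.2 percentage points. Its standard error would be √(0.064 × 0.936/125 + 0.032 × 0.968/125) = 0.027, giving a 95% CI of about −2.1 to 8.5 points (Fisher P = 0.38). Such a result describes the data and cannot settle the comparison.

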## **AIM OF THE WORK**

The aim of this study is to compare Incidence of cesarean scar defect in cases of cesarean section with and without bladder flap dissection.

## PATIENTS

This study will be prospectively conducted on 250 women recruited from ElShatby university maternity hospital delivery ward; They will be randomized into two groups group (A) and group (B) by closed envelop randomization. Group (A) will undergo cesarean section with bladder dissection and group (B) will undergo cesarean section without bladder dissection.

## **Inclusion Criteria:**

1- Patients who will undergo cesarean section for the first time (primi section)

## **Exclusion Criteria:**

- 1- Patient with excessive adhesion that necessitate bladder dissection
- 2- Previous uterine surgery e.g. myomectomy
- 3- Patient with comorbidities affecting wound healing e.g. diabetes, autoimmune diseases, immunosuppression
- 4- Patient in active labour with cervical dilatation > 5cm

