## **METHODS**

The patients will be randomized into two groups by closed envelop randomization; group (A) will undergo cesarean section with bladder dissection and group (B) will undergo cesarean section without bladder dissection.

All patients will be subjected to the following:

- 1- Complete history taking (gynecological, obstetric, medical, surgical)
- 2- Cesarean section using Joel-Cohen incision :
  - Joel-Cohen skin incision(straight skin incision 3 cm below the line connecting the anterior superior iliac spines)
  - Blunt dissection of the subcutaneous layer
  - Blunt extension of the fascial opening
  - Blunt entry into the peritoneum
  - Sharp superficial then blunt entry into the uterus
  - Spontaneous removal of the placenta
  - Double layer closure of the uterus
  - Non-closure of the peritoneum
  - Continuous closure of the fascia
  - Continuous suture of the skin

Group (A) will be subjected to bladder flap dissection after blunt entry to peritoneum and before sharp entry to uterus, while group (B) will undergo traditional steps with sharp and blunt entry into uterus directly after blunt entry into peritoneum After 3 and 6 months all patients will be subjected to Two-dimensional trans vaginal ultrasound:

Women will be examined after emptying their bladder. The uterus and uterine scar will be examined in the mid sagittal plane. A niche is defined as an anechoic space at least 2 mm deep at the presumed site of the cesarean section scar.

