# **RESULTS**

The results will be tabulated and statistically analyzed, using the standard statistical methods.

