### II-Comparison between two groups as regard obstetric history

Gravidity in group I had mean value  $1.44\pm1.03$  and in group II had mean value  $1.312\pm0.737$ . Parity in group I had mean value  $0.136\pm0.68$  and in group II had mean value  $0.192\pm0.73$ . It was found that most of cases had no abortion in two studied groups 97(77.6%) and 99(79.2%) respectively. No ectopic cases was higher with 125(100%) and 124(99.2%) respectively. Gestational age had mean value  $37.41\pm2.37$  and in group II had mean value  $36.99\pm2.50$ .

[figure not shown]
There were no statistically significant differences between the two studied groups regarding gravidity (P = 0.133), parity (P = 0.069), abortion (P=0.465), ectopic (P=0.159) and gestational age (P = 0.175). (Table 2, Fig. 15)

[figure not shown]
Obstetric history	Group I	Group II	T test P value
Gravidity			
Range	1-9	1-6	0.133
Mean	1.44	1.312	0.155
SD	1.03	0.77	
Parity			
Range	0-6	0-4	0.069
Mean	0.142	0.192	0.009
SD	0.68	0.73	
Abortion			
No	97 (77.6%)	99 (79.2%)	0.465
1-2	27 (21.6%)	23 (18.4%)	0.403
>2	1 (0.8%)	3 (2.4%)	
Ectopic			
No	125(100.0%)	124 (99.2%)	0.159
Yes	0.0 (0.0%)	1 (0.8%)	
Gestational age			0.175

[figure not shown]
Table (2): Comparison between the two studied groups regarding obstetric history.

Range	34-41	33-41	
Mean	37.41	36.99	
SD	2.37	2.50	

Group I. cesarean section with bladder dissectiont-test = student t-testGroup II: cesarean section without bladder dissection p was significant if  $\leq 0.05$ 

[figure not shown]

Figure (15): Comparison between the two studied groups regarding obstetric history.

[figure not shown]

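### Labour state is only partly restricted by the exclusion criteria and is not used in randomisation, shown by arm or adjusted for, so chance imbalance cannot be checked and some precision is lost

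*Protocol*

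**What the plan says.** The protocol's section on factors affecting the lower uterine segment states: "Cervical dilatation of > 5 cm, > 5 h duration of labour and advanced fetal station predispose to large niche". The next section, on level of incision, adds: "Cesarean section done in advanced labour after cervical effacement and also creation of uterovesical fold of peritoneum influence the level of uterine incision".

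The Inclusion Criteria admit any first cesarean. Of the labour factors, the Exclusion Criteria use dilatation alone: "Patient in active labour with cervical dilatation > 5cm". Neither hours in labour nor station is limited.

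On allocation, METHODS says: "The patients will be randomized into two groups by closed envelop randomization". No strata or blocks are described there or under PATIENTS. On analysis, the protocol's RESULTS section says only: "The results will be tabulated and statistically analyzed, using the standard statistical methods".

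The SAP document is written as a results chapter. Sections I and II compare age, gravidity, parity, abortion, ectopic pregnancy and gestational age, and section II concludes: "There were no statistically significant differences between the two studied groups regarding gravidity", and likewise for the other items. Section III compares uterine position. Section IV (Table 4) compares niche incidence by an unadjusted chi-square test. No table shows labour state, hours in labour, dilatation or station.

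**The concern.** The protocol treats labour as relevant to scar healing and excludes on one aspect of it, so the remaining variation in labour is a candidate prognostic factor by the protocol's own account. It is also largely known at enrolment, because the exclusion cannot be applied without knowing who is in active labour and how dilated she is. Despite that, the factor is left to unstratified allocation and then disappears from the report.

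Two things are at stake. First, a reader cannot tell whether the arms were alike on labour. The baseline tables cover mostly variables that the protocol does not list as niche risk factors; uterine position is the only listed one shown. Second, if labour does predict niche, ignoring it leaves avoidable variance in a comparison whose observed difference is small relative to its standard error.

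**Working it through.** **Printed comparison (SAP Table 4).** Niche present: 35 (28.0%) with bladder dissection, 26 (20.8%) without. Both percentages use 125 as denominator: 35/125 = 0.280 and 26/125 = 0.208, a difference of 7.2 points. (Present plus absent in the first group is 35 + 89 = 124; with 124 the difference would be 7.4 points. The printed percentages are used here.)

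**Crude standard error of that difference.**
√[(0.280 × 0.720 + 0.208 × 0.792)/125] = √(0.3663/125) = 0.054, or 5.4 points. The 95% half-width is 1.96 × 5.4 = 10.6 points.

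**Assumptions (not in the documents).** Share of women in labour q = 30–50%. Labour raises niche risk by d = 10–30 points among women eligible at 5 cm or less.

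**Chance imbalance in labour, simple 1:1 allocation, 125 per arm.** SE = √[2q(1−q)/125].
- q = 0.3: √(0.42/125) = 5.8 points; × 1.96 = 11.4 points
- q = 0.5: √(0.50/125) = 6.3 points; × 1.96 = 12.4 points

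**Resulting shift in the niche difference (imbalance × d).**

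| | d = 10 points | d = 30 points |
|---|---|---|
| One SE, q = 0.3 | 0.6 | 1.7 |
| One SE, q = 0.5 | 0.6 | 1.9 |
| 95% limit, q = 0.3 | 1.1 | 3.4 |
| 95% limit, q = 0.5 | 1.2 | 3.7 |

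**Share of variance explained by labour.** R² = q(1−q)d²/(0.244 × 0.756), where 0.244 = 61/250 is the pooled niche rate.
- Lowest (q = 0.3, d = 0.10): 0.0021/0.1845 = 0.011
- Highest (q = 0.5, d = 0.30): 0.0225/0.1845 = 0.122

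Adjustment is therefore worth an effective sample size of about 250/(1 − 0.011) = 253 to 250/(1 − 0.122) = 285. At best the standard error falls from 5.4 to about 5.4 × √0.878 = 5.1 points.

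**Cross-check on a different scale.** With q = 20–50% and an odds ratio of 1.5–5 at the same pooled rate, the 95% shift is 0.8–3.6 points and the effective sample size 251–282. At an odds ratio of 3 the 95% shift is 2.3–2.5 points.

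**How demanding the upper end is.** A 30-point effect at a pooled rate of 0.244 means risks of 0.154 and 0.454 when q = 0.3 (odds ratio 4.6), or 0.094 and 0.394 when q = 0.5 (odds ratio 6.3). The largest odds ratio the protocol quotes for any niche risk factor is 3.14, for previous cesarean.

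**The case against.** The strongest reply is that randomisation already deals with this. Chance imbalance in labour is one component of the crude standard error and not an error on top of it, so the crude test is valid without adjustment. That is correct, and it limits the point to checkability and precision.

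Four stronger readings are tempting, and the documents do not support them.

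- A reader might infer that labour confounds the comparison because, in the protocol's account, advanced labour and the uterovesical fold both influence incision level. A shared pathway does not create confounding between randomised arms. The passage also concerns advanced labour after effacement, much of which the dilatation exclusion probably removes, along with some long labours and advanced stations.
- A reader might infer that labour is a strong cause of the outcome. The protocol links the three factors to large niches, which it defines by residual myometrium. The outcome compared is any niche at least 2 mm deep. Nothing quantifies the effect of labour at 5 cm or less on that outcome.
- A reader might infer that every listed risk factor was ignored. Uterine position is tabulated, and retroflexion is a listed factor. Previous cesarean, diabetes and uterine closure are handled by eligibility or a common technique.
- A reader might infer that labour explains the non-significant result, since 7.2 + 3.7 = 10.9 points, and 10.9/5.4 is about 2. This needs the largest assumed effect, half the women in labour and an imbalance at its 95% limit. The direction is unknown; the opposite imbalance would give 7.2 − 3.7 = 3.5 points.

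It is also fair to say that a mixed first-cesarean population is a legitimate choice. The mixing is permitted by the criteria; the documents do not show how much occurred.

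**Conclusion.** The point holds as a moderate weakness of design and reporting. One of three named labour factors is restricted, and the remaining variation is neither balanced by design, nor shown by arm, nor adjusted for.

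No bias in expectation follows if allocation was sound. On the assumed inputs, a typical chance shift is under 2 points and an extreme one under 4, against a difference of 7.2 points whose 95% half-width is about 10.6. The gain in precision from using labour state ranges from negligible to modest. These sizes rest wholly on the assumed share in labour and the assumed labour effect; the text findings do not depend on them.

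**What to change.** **If enrolment is open:** keep separate envelope sets for women in labour and not in labour, each prepared in blocks. Separate sets without blocks do not secure balance. Prespecify that the niche comparison is adjusted for that stratum.

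**If enrolment is complete, as the SAP document's results suggest:** add labour state (yes/no) and last dilatation to the baseline table by arm, with hours in labour and station if they were recorded. Report the labour-adjusted niche difference beside the crude one and label it a post hoc sensitivity analysis, since the crude result is already known. If labour data cannot be recovered, state that balance on labour could not be assessed.

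Neither route changes eligibility or clinical care. The cost is a second set of envelopes or some chart abstraction, plus one more estimate to explain. No extra patient, visit or procedure is needed.
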